7.7.5.2 To evaluate renal and hepatic safety parameters over time

Proportion of patients having adverse events related to hepatic and renal functions that are considered to be related to study drug over the period up to 5 years from the start of deferasirox treatment will be calculated.

For laboratory parameters directly related to hepatic parameters: ALT, AST, total bilirubin, alkaline phosphatase and directly related to renal parameters: serum creatinine, creatinine clearance; observed values (and changes from baseline) averaged at baseline, after first intake of study medication to day 30, day 31 to day 90 and per subsequent quarter will be summarized by descriptive statistics (n, mean, standard deviation, minimum, lower quartile, median, upper quartile and maximum).

In addition to the above mentioned tables and listings, other exploratory analyses, for example, figures plotting time course of raw or change in laboratory tests over time or box plots, will be specified in the Statistical Analysis Plan (SAP).

7.7.5.2.1 Supportive analyses

However, in case of a high number of missing values, supplementary analyses using Complete Case Analysis approach will be performed. A Complete Case Analysis excludes cases with missing laboratory values (for main hepatic and renal parameters) so that only complete cases are available. The estimates obtained from the complete case analysis shall be compared with the overall data set to view the effect of missing values on the estimates. If the number of patients to be included in this analysis is low, the analysis will not be conducted.

7.7.5.3 To evaluate growth by gender

The time-course of weight, height and BMI and its absolute or relative changes from baseline, as appropriate will be summarized on Safety Set using descriptive statistics.

All individual trajectories for weight, height and BMI will be superimposed on a graph with CDC US growth chart percentiles (5th, 25th, 50th, 75th, 95th), available for patients from 10 to 20 years.

In addition, weight, height and BMI will be flagged according to these percentile categories [0- 5^{th}); $[5^{th} - 25^{th}]$; $[25^{th} - 50^{th}]$; $[50^{th} - 75^{th}]$; $[75^{th} - 100^{th}]$ and shift tables will be provided to compare baseline to the last available value on study.

Summary statistics of the height, weight and BMI standard deviation scores (SDS) for baseline, end of each year as well as end of study and change from baseline by gender and age category at enrollment (10 - < =12, >12 - < 18) will be provided.

In addition, weight, height and BMI will be plotted by age category at the time of assessment for E2422, and the same analysis will be done for study ICL670A107E for the same age category patients as E2422. ICL670A107E is a registry study with the historical data from the four-year follow-up of the premarket clinical trial for children with β-thalassemia who are on a regular transfusion program.

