Addition of timeframe: The current version of the protocol defines baseline as "the point in time when the patient starts treatment with deferasirox (Section 7.1)". In addition, protocol

ICL670/ deferasirox/CICL670E2422

Page 21

states that "data will be collected from the start of deferasirox treatment (baseline) and then on for up to five years (Sections 7.1, 7.3, 7.7)". Of note, there is no guidance in the protocol on timeframe prior to start date of deferasirox treatment during which baseline data may be collected. The current wording of the protocol has created confusion and inconsistencies in the way baseline data is collected. Investigators have applied their own interpretation on baseline data definition and have been reporting what is requested by the protocol as baseline, including data on or prior to the start date of deferasirox. The protocol is amended to correct this deficiency to allow a consistent approach, and to implement a timeframe around the baseline assessment data collection.

- Clarification has been provided on what will be considered as post-baseline safety assessment for inclusion in the safety set.
- Stopping rule: The protocol currently mandates stopping rules for deferasirox treatment based on serum ferritin levels, which in the context of a non-interventional study seems inappropriate since these cannot be enforced. In the study, patients are treated based on investigator judgement following local practices. The stopping rules remain in the protocol as a recommendation to investigators.
- In order to correct inconsistencies in the protocol regarding age categories and to align with the age group population defined in the study section 7.2, the analyses for growth and sexual development by age categories were reduced from 3 categories (10 -<12, 12-<16, 16-<18 as in current protocol) to two categories (10-<=12, >12-<18). This modification is implemented considering that relatively small number of patient in the study, having three age subgroups will lead to small number of patients in each age category and to imprecise results. Furthermore, the 10-<=12 category (approximately half of the patients enrolled) represents an adequate group to assess the impact that deferasirox may have on growth and development.
- Table 3.1: Study protocol amendment and updates have been updated to include reasons for changes in protocol amendment 3.1 and 4.0.

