7.1 Study design

This study is a registry of pediatric patients with non-transfusion dependent thalassemia conducted in response to a post-approval commitment to the US FDA for an observational study in this population in order to assess long-term exposure and safety of deferasirox. (PMR 1994-4: "Establish a registry of children (aged 10 to <18 years old at enrollment) with NTDT and treated with deferasirox for documented iron overload. Study CICL670E2422 will follow at least 40 children for up to 5 years to assess and analyze the long-term safety of treatment with deferasirox, including an assessment of growth, compared to children on a regular transfusion program receiving deferasirox (based on historical data)").

This study is non-interventional and does not impose a therapy protocol, diagnostic/therapeutic interventions or a visit schedule. However, a minimum of quarterly visits are suggested. Patients

will be treated with deferasirox in accordance with the local (country-specific) deferasirox prescribing information.

The definition of non-interventional study is provided in Article 21 of Directive 2001/20/EC: "A study where the medicinal product(s) is (are) prescribed in the usual manner in accordance with the terms of the marketing authorization. The assignment of the patient to a particular strategy is not decided in advance by a study protocol but falls within the current practice and the prescription of the medicine is clearly separated from the decision to include the patient in the study. No additional diagnostic or monitoring procedures shall be applied to the patients and epidemiological methods shall be used for the analysis of the collected data". In this context it is considered important to clarify that interviews, questionnaires and blood samples may be considered as normal clinical practice (EMEA 2008).

The study will take place in actual practice setting and will monitor patients treated with deferasirox according to the local (country-specific) prescribing information. The study will be based on primary data collection directly from healthcare professionals.

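### The growth comparison with historical transfused children rests on plots with no standardisation stated, so a difference in age mix can look like a growth difference; separately, the percentile reference ends at age 20

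*Protocol*

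**What the plan says.** Protocol section 7.1 quotes the US post-approval commitment. It asks for long-term safety, "including an assessment of growth, compared to children on a regular transfusion program receiving deferasirox (based on historical data".

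The historical study enters the analysis in one place, the last paragraph of section 7.7.5.3: "weight, height and BMI will be plotted by age category at the time of assessment for E2422, and the same analysis will be done" for ICL670A107E, limited to patients in the same age category. The comparator is described thus: "ICL670A107E is a registry study with the historical data from the four-year follow-up of the premarket clinical trial". The sentence names weight, height and BMI, and mentions no SDS, percentile or change from baseline.

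The paragraph before it plans a standardised summary: "Summary statistics of the height, weight and BMI standard deviation scores (SDS) for baseline, end of each year as well as end of study", with "change from baseline by gender and age category at enrollment (10 - < =12, >12 - < 18) will be provided". It does not mention ICL670A107E.

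The same section also plans individual trajectories against CDC percentile curves, described as "available for patients from 10 to 20 years". Percentile categories are to be compared in shift tables between baseline and the patient's final on-study measurement. Sections 7.1 and 7.2 admit patients from age 10 to under 18 at enrollment and follow them for up to 5 years from the start of deferasirox.

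**The concern.** This is the only between-cohort comparison in the study, and the commitment names it. Height, weight and BMI all change with age through puberty, so a comparison of unstandardised values within a wide age band mixes growth with age. Either a reassuring or an alarming picture could be produced by age mix alone.

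The protocol's own background makes an age imbalance plausible. Section 7.2 says that patients with non-transfusion-dependent disease tend to show iron overload later in life than transfusion-dependent patients. Section 7.1 gives approval from age 2 for transfusional overload but from age 10 for the non-transfusion-dependent indication.

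A second, smaller matter concerns the E2422 growth tables only. The percentile reference stops at an age that some patients will pass, and the shift tables take the final measurement whatever the age.

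**Working it through.** The protocol gives no figure for the growth comparison, so there is none to reproduce. Its one design calculation, the detection probabilities in section 7.5, reproduces as 1 − (1 − p)^40 (for example 0.87 at p = 5%) and does not bear on this point.

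**1. What is standardised, and for whom**

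| Analysis in 7.7.5.3 | E2422 | ICL670A107E |
|---|---|---|
| Weight, height, BMI plotted by age category at assessment | yes | yes |
| SDS and change, by gender and age category | yes | not stated |
| CDC percentile flags and shift tables | yes | not stated |

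The only analysis stated for both cohorts is the one with no standardisation stated.

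**2. Size of an age-mix effect.** Band widths: 12 − 10 = 2 years and 18 − 12 = 6 years. Shift in mean height = growth rate × difference in mean age. Assumptions not in the documents: growth of 2 to 6 cm/year in the upper band and a height SD of 7 cm.

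- 1-year difference: 2 × 1 to 6 × 1 = 2 to 6 cm, or 2/7 to 6/7 = 0.3 to 0.9 SD.
- Half-year difference: 1 to 3 cm.
- 2-year difference: 4 to 12 cm.

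**3. Against sampling error.** The protocol requires at least 20 patients per age category. Assume 20 E2422 patients, 20 to 100 comparators and an SD of 7 to 8 cm. The 95% half-width of a mean height difference is 1.96 × SD × √(1/20 + 1/n).

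- SD 7, n = 100: 1.96 × 7 × √0.06 = 3.4 cm.
- SD 8, n = 20: 1.96 × 8 × √0.10 = 5.0 cm.

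A 1-year age difference can therefore be as large as, or larger than, the sampling error.

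**4. Ages beyond the bands and the reference.** A patient just under 18 at the start who completes 5 years ends at almost 18 + 5 = 23. Anyone starting after 20 − 5 = 15 and completing 5 years passes age 20. Both scenarios below assume that all patients complete 5 years.

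| Assumed starting ages | End above age 20 | Person-time above 20 | Person-time at 18 or over |
|---|---|---|---|
| Half uniform on 10–12, half uniform on 12–18 | 0.5 × 3/6 = 25% | 7.5% | 21% |
| Uniform on 10–18 | 3/8 = 37.5% | 11% | 31% |

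The bands given in the section stop below 18, so the assessments in the last column have no stated category if those bands are used for the plot.

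**The case against.** The strongest defence is that the study is descriptive by design. Growth is a secondary objective, the commitment prescribes no estimator, and side-by-side plots are a comparison of a kind. E2422 growth is already assessed by SDS, percentile shifts and individual trajectories. The protocol also limits ICL670A107E to the same age categories, and the move to two bands was explained by numbers: "having three age subgroups will lead to small number of patients in each age category and to imprecise results". Further detail is left to the SAP.

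Much of this is fair, and it rules out several stronger readings that a reader might infer.

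- *That age and sex mix will drive the comparison.* The age and sex composition of ICL670A107E is not given, so only the possibility is supported.
- *That the sexes are pooled.* The plot sentence does not mention gender, but the section heading and the objective in Table 6-1 do. Pooling is not established.
- *That the plot uses exactly the two bands and drops every assessment at 18 or over.* The bands are stated for age at enrollment. Their use for age at assessment is an inference, and the person-time figures depend on it.
- *That end-of-study SDS cannot be computed for the oldest patients.* The 10-to-20 range is attached to the CDC percentile chart, and no reference is named for the SDS.
- *That an adjusted mean difference with a confidence interval is required.* That goes beyond a plan that is descriptive for all endpoints.

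The core remains. The protocol itself chooses the measure for the historical comparison, so this is not a detail left to the SAP. Matching on a six-year band does not match on age within it. Few patients per band is a reason to standardise for age, and SDS does so without splitting the sample further.

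**Conclusion.** The point holds in a limited form. The one comparison that the commitment asks for is fixed as a plot of measures with no standardisation stated, although an age- and sex-standardised measure is already planned for one of the two cohorts. With a six-year upper band, a 1-year difference in mean age could shift mean height by 2 to 6 cm, against a sampling half-width of about 3.4 to 5.0 cm. These sizes rest on assumed growth rates, SDs and comparator numbers, and on the section's bands being used for the plot. Whether an age difference exists cannot be read from the protocol.

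The age-20 limit is a separate and smaller defect in the E2422 percentile flags and shift tables, and it does not touch the historical plot. Some 25% to 37.5% of 5-year completers would pass age 20 under the two assumed age distributions. The share of all patients would be smaller, because follow-up is up to 5 years and section 7.3 withdraws patients who stop deferasirox permanently for reasons other than the stopping rule.

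The primary variable, drug-related serious adverse events, is unaffected.

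**What to change.** 1. Apply the height, weight and BMI SDS summaries planned for E2422 to ICL670A107E patients of the same starting ages. Give the value and the change from the start of deferasirox, by sex and age category, at years 1 to 4, and present them descriptively beside E2422. Four years is the common span, since the comparator consists of "historical data from the four-year follow-up of the premarket clinical trial".
2. Keep the plots of weight, height and BMI as supplementary output, by sex, with a category for assessments at age 18 and over.
3. For percentile flags and shift tables, and for SDS if CDC is the reference, use the last measurement within the reference range as the final value. Name the SDS reference.

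The cost is a change of wording and some programming, with no new data collection in E2422. The sponsor should confirm that the historical file holds sex, age and a measurement at the start of deferasirox. The downside is that year 5 and measurements after age 20 do not enter these standardised comparisons. SDS will also not remove differences between the cohorts in disease or transfusion, so the comparison stays descriptive.

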7.7.5.4 To evaluate sexual development by gender

Shift tables for Tanner stages to compare baseline to the last on-study value will be provided. Descriptive statistics will be also provided for age at assessment for each Tanner stage.

Number and percentages of patients who are below, within and above the Marshal standards (Marshall and Tanner 1970) (mean age \pm 2 SD) for each Tanner stages by gender will be provided.

The age of patients at time they reach the next Tanner stage will be flagged based on the Marshal standards and the listing will be provided.

Number and percentage of patients at different Tanner stages will be provided by gender and baseline age category (10 - < = 12, > 12 - < 18) at enrollment, at the end of each year and at end of study.

To evaluate long term efficacy of deferasirox as measured by serum 7.7.5.5 ferritin and LIC

The time-course of serum ferritin and LIC and its absolute/relative changes from baseline will be summarized on FAS using descriptive statistics quarterly.

Counts and frequencies will be provided on FAS for patients:

- achieving a SF <300 ng/mL at any time during study;
- achieving LIC <3 mg Fe/g dw at any time during study;
- restarting deferasirox treatment after temporary interruption due to one of the two criteria mentioned above (SF <300 ng/mL or LIC <3 mg Fe/g dw at any time during study).

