Serum ferritin (SF) has been traditionally used to assess transfusional iron overload with a wellestablished correlation to liver iron concentration (LIC), a more direct measurement of liver tissue iron. However, SF levels have recently been reported to underestimate LIC in patients with NTDT as compared to regularly transfused patients (Origa R, et. al., Haematologica 2007; Pakbaz Z, et. al., Pediatr Blood Cancer 2007; Taher A, et. al., Haematologica 2008). Magnetic resonance imaging (MRI) is a sensitive and specific tool for non-invasively assessing hepatic iron overload (Clark P and St. Pierre T, Magnetic Resonance Imaging 2000; St Pierre T and Clark P, et. al., Blood 2005).

NTDT patients whose LIC levels ≥5 mg Fe/g dry weight (or serum ferritin level >800 ng/mL) are at higher risk of developing iron-related morbidity (Musallam K, et. al., Blood Cells Mol Dis. 2013; Blood Reviews 2012). The use iron chelation therapy in NTDT has been documented in previous reports and small uncontrolled studies (Olivieri 1992; Rombos 2000; Pootrakul 2003; Taher et. al., Blood 2010) and recommended by Thalassemia International Federation (Guidelines for the Management of NTDT, 2013).

Out of three available chelators, deferasirox is the only drug that has been evaluated in a randomized clinical study in patients with NTDT (No CICL670E2209, the THALASSA study).

In this study, deferasirox compared with placebo, at starting doses of 5 and 10 mg/kg/day with dose escalations up to 20 mg/kg/day in patients with high levels of iron overload (LIC \geq 5 mg Fe/g dw and SF >300 ng/mL) significantly reduced LIC and SF levels after one year of treatment. Based on the results of this study deferasirox has been recently approved by FDA and EU for the treatment of iron overload in this population (Taher A, et. al., Blood 2012).

In addition, the 1-year extension study of THALASSA showed that NTDT patients receiving deferasirox for up to 2 years continue to respond with decreases in LIC and serum ferritin. More patients reached LIC <5 and <3 mg Fe/g dw during the extension indicating that with appropriate dosing and treatment deferasirox continues to effectively remove iron (Taher A, et. al., poster 3258; ASH 2012).

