Non-interventional study (NIS)' in this context is used synonymously with 'observational study', i.e., does not involve any kind of intervention, experimental or otherwise. In these studies, interviews, questionnaires and blood samples may be performed as normal clinical practice.

6 Research question and objectives

This observational study will evaluate the long term safety of deferasirox therapy in pediatric patients ≥ 10 to ≤ 18 years at enrollment with NTDT in actual practice setting.

Table 6-1 Objectives and Endpoints

Objectives	Endpoints	Analysis
Primary		
Evaluate the long term safety of deferasirox	Proportion of patients having SAEs that are considered to be related to study drug up to 5 years from the start of deferasirox treatment	Section 7.7.4
Secondary		

Evaluate the incidence of serum creatinine and SGPT (ALT) increases in actual practice setting	The proportion of patients having (up to 5 years from the start of deferasirox treatment): Serum creatinine > 33 % above baseline and above the age adjusted ULN in at least two consecutive post-baseline measurements at least 7 days apart from each other. SGPT (ALT) above 5 x ULN in at least two consecutive post-baseline measurements at least 7 days apart from each other	Section 7.7.5.1
Evaluate renal and hepatic safety parameters over time	Absolute/relative changes from baseline of SGPT (ALT), SGOT (AST), total bilirubin, alkaline phosphatase, serum creatinine, creatinine clearance quarterly up to 5 years. Proportion of patients having hepatic and renal clinical events that are considered to be related to study drug up to 5 years from the start of deferasirox.	Section 7.7.5.2
Evaluate growth by gender	Absolute change in BMI, weight and height from baseline to EOS Proportion of patients falling behind in growth based on height, weight and BMI	Section 7.7.5.3
Evaluate sexual development by gender	Mean age at assessment for each Tanner stage Changes from baseline to the last on-study value of all Tanner stage parameters.	Section 7.7.5.4
Evaluate long term efficacy of deferasirox as measured by serum ferritin and LIC	Absolute/relative change in SF and LIC from baseline to EOS Proportion of patient achieving a SF <300 ng/mL Proportion of patients achieving LIC <3 mg Fe/g dw Proportion of patients reinitiating deferasirox after discontinuation due to a "stopping rule" *	Section 7.7.5.5

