In NTDT, a combination of increased intestinal iron over-absorption and occasional transfusions results in an iron accumulation rate which is much slower than in patients with transfusion dependent thalassemias. As a result, patients with NTDT tend to present with some degree of iron overload later in their life compared to transfusion dependent patients. This fact limits the pool of patients who could potentially meet the eligibility criteria and be enrolled in to the study. Furthermore, the feasibility which was conducted in major thalassemia countries

confirmed the limited number of pediatric patients with NTDT who can be treated with deferasirox.

Patients will be enrolled if they meet the following criteria.

Inclusion criteria:

Patients eligible for inclusion in this study must meet all of the following criteria:

1. Male or female aged \geq 10 but <18 years old with non-transfusion-dependent thalassemia syndromes inclusive of beta-thalassemia intermedia, HbE beta-thalassemia or alpha thalassemia intermedia (HbH disease) and chronic iron overload

AND

2. Patients currently treated for a maximum of 12 months or patients planned to be treated with deferasirox

AND

3. Written informed consent obtained prior to any screening procedures. The consent form will be signed by the patient's legal guardian.

Exclusion Criteria

1. Patients treated with deferasirox in an interventional clinical study.

7.3 **Variables**

Treatment

Treating the Patient

The study being non-interventional, the patient will be treated at the physician's discretion and according to the local country-specific deferasirox prescribing information.

The starting dose of deferasirox, subsequent dose adjustments and treatment interruption will be at the physician's discretion and according to the local country-specific prescribing information and will be recorded on the Dosage Administration Record eCRF together with the reasons for the dose changes and interruptions.

Drug Compliance

The compliance will be assessed by caregiver interviews. The caregiver will be asked how many doses, if any, of deferasirox treatment was missed in the last treatment period.

Drug Accountability

Not applicable since commercial drug is used.

IWR (Interactive Web Response System)

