This study is a non-interventional study and therefore does not impose a treatment period. Patients will be treated with deferasirox according to the physician's judgment and in accordance with the local country-specific deferasirox prescribing information. The daily dose of deferasirox will be recorded by the physician and/or study personnel, this will include the initial dose of deferasirox and subsequent changes in dose. The maximum treatment duration of deferasirox treatment observed will be 5 years.

Compliance will be recorded by the physician from information provided retrospectively by the parent/caregiver.

Effectiveness

According to the general prescribing information for deferasirox, measurements of SF should be performed monthly to assess response to therapy and to evaluate for the possibility of overchelation of iron. All available SF values will be recorded.

Premature withdrawal

Patients must be withdrawn from the study if any of the following occurs:

Consent withdrawal

- Deferasirox treatment permanently stopped, except due to stopping rule.
- Patient participating in an interventional clinical trial

Patients may voluntarily withdraw from the study or be dropped from it at the discretion of the physician at any time.

For patients who are lost to follow-up, the physician should show "due diligence" by documenting in the source documents steps taken to contact the patient, e.g. dates of telephone calls, registered letters, etc.

Follow up period

Data will be collected on each patient for up to 5 years from the start of deferasirox treatment. There is no follow-up period after the 5 years unless the patient discontinued due to an adverse event (in this case refer to Section 9).

Assessment types

Safety

Patient safety will be monitored by reviewing medical and laboratory records and collecting available data on:

- SrCr, creatinine clearance, SF, urea, SGOT (AST), SGPT (ALT), alkaline phosphatase, bilirubin and proteinuria,
- LIC, CMR, echocardiography, ECG, vital signs,
- cardiac events potentially related to cardiac iron overload,
- height, weight, BMI,
- sexual development according to Tanner stage,
- audiometry and ophthalmology examination findings,
- concomitant medication at time of renal or hepatic AE,
- adverse event (AE)

For details on AE collection and reporting, refer to Section 9.

Laboratory evaluations

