7.7 Data analysis

This is a non-interventional pediatric study that does not impose a therapy protocol, diagnostic/therapeutic interventions or a visit schedule. Data will be collected on all eligible pediatric patients aged ≥ 10 to <18 years at enrollment with non-transfusion dependent thalassemia treated with deferasirox and will be followed for up to 5 years from the start of deferasirox treatment. Retrospective data collection will be done for patients who have started deferasirox 12 months or less prior to enrollment.

The baseline is defined as the timeframe before the patient starts treatment with deferasirox.

Post baseline data will be collected from the start date of deferasirox and then on for five years.

The data will be analyzed by Novartis and/or a designated CRO.

Continuous variables will be summarized by number of patients, mean, standard deviation, minimum, 25th-percentile, median, 75th percentile and maximum. Categorical variables will be summarized by absolute and relative frequencies.

In addition to the statistical methods outlined below, further details and any additional, exploratory analyses that may be performed will be described in the Statistical Analysis Plan (SAP).

7.7.1 **Analysis sets**

7.7.1.1 **Full Analysis Set**

The Full Analysis Set (FAS) comprises all patients who received at least one dose of deferasirox during the study.

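### Restart of deferasirox is reported over the whole FAS, so the percentage cannot show how often patients who stop under the stopping rule need to resume

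*Protocol*

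**What the plan says.** Section 7.7.5.5 (long-term efficacy by serum ferritin and LIC) opens its list of proportions with "Counts and frequencies will be provided on FAS for patients". Three items follow:

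- "achieving a SF <300 ng/mL at any time during study";
- the corresponding item for LIC <3 mg Fe/g dw;
- "restarting deferasirox treatment after temporary interruption due to one of the two criteria mentioned above".

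Section 7.7.1.1 defines the set: "The Full Analysis Set (FAS) comprises all patients who received at least one dose of deferasirox during the study". Section 7.7 says that categorical variables are given as absolute and relative frequencies.

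The endpoint in Table 6-1 is worded differently: "Proportion of patients reinitiating deferasirox after discontinuation due to a" stopping rule. Section 7.1 expects physicians to follow that rule and to reintroduce deferasirox if iron levels rise again. Section 7.3 exempts these patients from withdrawal; the withdrawal criterion reads "Deferasirox treatment permanently stopped, except due to stopping rule". The same section has the reasons for dose changes and interruptions recorded on the dosage eCRF.

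On iron status at entry, inclusion criterion 1 ends with "alpha thalassemia intermedia (HbH disease) and chronic iron overload" and gives no numeric SF or LIC floor. The statement of purpose and Section 5 add that the overload is documented according to the local label. Section 5 also notes that "SF levels have recently been reported to underestimate LIC in patients with NTDT as compared to regularly transfused patients".

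**The concern.** The restart endpoint is the one planned summary of what happens after a patient reaches target and stops. The patients who can restart are those who stopped under the rule. The protocol keeps them under observation, yet no planned proportion uses them as its denominator. Over the FAS, a low figure could mean that few patients stopped or that few of those who stopped had to resume, and the percentage alone cannot separate the two.

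The wording adds a second difficulty. Discontinuation under the stopping rule and a temporary interruption are not the same event. If an interruption is called temporary because treatment resumed, it cannot serve as the denominator.

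A lesser matter is that the two attainment items ask only for a value below the threshold at some time during the study. They do not require that the patient started at or above it.

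**Working it through.** **Inputs.** N = 40 is the planned minimum (Section 7.5), taken here as the FAS size. The protocol gives no expected number stopping, restarting, starting below threshold or unmeasured, so those values below are assumptions. It states no figure for these endpoints. Its only computed table, the detection probabilities in Section 7.5, reproduces from 1 − (1 − p)^40 (for example 0.87 at 5%) but does not bear on this point.

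**Restart.** Let s be the number stopped under the rule and r the number of those who restarted. Then

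r/N = (s/N) × (r/s).

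The FAS figure can never exceed s/N. One FAS figure fits very different restart rates:

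| Stopped s | Restarted r | r/N (FAS) | r/s (stoppers) |
|---|---|---|---|
| 4 | 4 | 10% | 100% |
| 8 | 4 | 10% | 50% |
| 16 | 4 | 10% | 25% |
| 20 | 4 | 10% | 20% |

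Conversely, one restart rate among stoppers gives different FAS figures. If half restart, the FAS figure is 4/40 = 10%, 8/40 = 20% or 10/40 = 25% when 8, 16 or 20 have stopped.

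**Wording of the event.** If a temporary interruption is recognised by the later restart, the number of temporary interrupters equals r, and r/r = 100%. Moving from the FAS to the Section 7.7.5.5 event as denominator would therefore give close to 100% by construction. The Table 6-1 event, a stop under the rule, does not have this defect if every such stop is counted.

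**Attainment.** Let b be the patients already below the threshold before treatment and a those newly reaching it. As worded, the FAS figure is (a + b)/N. Among patients starting at or above the threshold it is a/(N − b). With a = 8:

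| b | (a + b)/N | a/(N − b) |
|---|---|---|
| 0 | 8/40 = 20% | 8/40 = 20.0% |
| 2 | 10/40 = 25% | 8/38 = 21.1% |
| 4 | 12/40 = 30% | 8/36 = 22.2% |
| 8 | 16/40 = 40% | 8/32 = 25.0% |

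Each such patient adds 1/40 = 2.5 points to the FAS figure. With a = 0 and b = 4 it would be 10% although nobody newly reached target.

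**Missing measurements act in the other direction.** Section 7.3 collects LIC only when available. If 12 patients attain the target and 16 of 40 have no post-baseline value, the FAS figure is 12/40 = 30%, against 12/24 = 50% of those measured.

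**The case against.** The best defence is that naming the FAS only fixes the analysis set, and that the SAP, to which Section 7.7 defers further details, may add a row over the patients who stopped. Counts accompany percentages, and Section 7.7.3 summarises the number of interruptions and their reasons. The endpoints are secondary and purely descriptive. This limits the weight of the point but does not remove it. The protocol states a denominator rather than leaving it open. The Section 7.7.3 summary is on the Safety Set and is not expressly a count of patients stopped under the rule, so a reader may be unable to rebuild the proportion from it.

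A second defence is that Section 9 lists temporary interruption and permanent discontinuation as separate recorded actions for adverse events, so temporary need not be defined by a later restart. That is fair, but Table 6-1 and Section 7.7.5.5 still name different events.

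Four stronger readings are tempting, and the documents do not support them:

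- *The FAS restart figure measures how many stopped.* It is a product: 20 stopped with 4 restarted gives 10%, not 50%.
- *Patients already below target will be counted as successes.* This is possible but not shown. Entry requires overload by local-label criteria, which are not reproduced; achieving a value can be read as a new event; and no baseline distribution is given.
- *The same applies equally to LIC.* The remark that SF underestimates LIC makes a low SF with a raised LIC plausible. It offers no mechanism for a baseline LIC <3.
- *A low figure will be taken as lasting iron control off drug.* Nothing in the protocol says how the figure would be interpreted.

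**Conclusion.** The restart point holds. The planned percentage on the FAS mixes reaching a stop with resuming after it and cannot answer how often patients who stop need to resume. In the cases worked, one value of 10% is compatible with restart rates from 20% to 100% among stoppers. The algebra needs no assumption; those particular rates rest on assumed numbers stopping among 40. The two descriptions of the event also need reconciling.

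The attainment point is conditional. The wording has no baseline requirement, so any patient below threshold before treatment would count, at 2.5 points each. The number of such patients is unknown and may be zero. Unmeasured patients pull the FAS figure the other way, so the net direction cannot be stated.

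The primary endpoint and the study size are unaffected.

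**What to change.** In Table 6-1 and Section 7.7.5.5:

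1. Use one description of the event in both places. Report restart as n over all patients whose deferasirox was stopped with SF <300 ng/mL or LIC <3 mg Fe/g dw as the recorded reason, whether or not they later restart. Keep n/FAS beside it.
2. Give the length of follow-up after stopping, since a patient who stops near the end of the five years has little time to restart. A time-to-restart display is optional; with a handful of stoppers it is a matter of preference.
3. Report attainment of each threshold among patients with a baseline value at or above it and at least one post-baseline value. Show separately those below threshold at baseline, those with no baseline value, and those with no post-baseline value.

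This costs some wording and changes to the table shells. It needs no new assessments, provided the eCRF reason field identifies stops for these two criteria. None of it touches how patients are treated.

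The downside is precision. For 4 restarts, the exact 95% interval is 2.8% to 23.7% over 40 patients, but 15.7% to 84.3% over 8 stoppers. Attainment denominators will also shrink, because baseline laboratory values count only within 1.5 months before the start of treatment and LIC is collected only when available. Listing the excluded groups makes that loss visible.
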